Appendix 1. ECOG Performance Status

Grade	ECOG
0	Fully active, able to carry on all pre-disease activities without restriction.
1	Restricted in physically strenuous activity but ambulatory and able to carry out work of a light or sedentary nature, eg, light house work or office work.
2	Ambulatory and capable of all selfcare but unable to carry out any work activities. Up and about more than 50% of waking hours.
3	Capable of only limited selfcare, confined to bed or chair more than 50% of waking hours.
4	Completely disabled. Cannot carry on any selfcare. Totally confined to bed or chair.
5	Dead.

Appendix 2. Table of French-American-British (FAB) classification of Acute Myeloid Leukemia

Acute Myeloid Leukemia (AML) Diagnosis	FAB Classification
Myeloblastic leukemia minimally differentiated	M0
Myeloblastic leukemia without maturation	M1
Myeloblastic leukemia with maturation	M2
Hypergranular promyelocytic leukemia	M3
Variant, microgranular promyelocytic leukemia	M3V
Microgranular variant Myelomonocytic leukemia	M4
With bone marrow eosinophilia	M4Eo
Monocytic Leukemia	M5
Poorly differentiated	M5a
Differentiated	M5b
Erythroleukemia	M6
Megakaryoblastic Leukemia	M7

Appendix 3. WHO Classification of Myelodysplastic Syndromes (MDS)

Disease	Blood findings	Bone marrow findings
Refractory anemia (RA)	Anemia No or rare blasts	Erythroid dysplasia only < 5% blasts < 15% ringed sideroblasts
Refractory anemia with ringed sideroblasts (RARS)	Anemia No blasts	Erythroid dysplasia only ≥ 15% ringed sideroblasts < 5% blasts
Refractory cytopenia with multilineage dysplasia (RCMD)	Cytopenias (bicytopenia or pancytopenia) No or rare blasts No Auer rods < 1 × 10 ⁹ /L monocytes	Dysplasia in ≥ 10% of cells in 2 or more myeloid cell lines < 5% blasts in marrow No Auer rods < 15% ringed sideroblasts
Refractory cytopenia with multilineage dysplasia and ringed sideroblasts (RCMD-RS)	Cytopenias (bicytopenia or pancytopenia) No or rare blasts No Auer rods < 1 × 10 ⁹ /L monocytes	Dysplasia in ≥ 10% of cells in 2 or more myeloid cell lines ≥ 15% ringed sideroblasts < 5% blasts No Auer rods
Refractory anemia with excess blasts-1 (RAEB-1)	Cytopenias < 5% blasts No Auer rods < 1 × 10 ⁹ /L monocytes	Unilineage or multilineage dysplasia 5% to 9% blasts No Auer rods
Refractory anemia with excess blasts-2 (RAEB-2)	Cytopenias 5% to 19% blasts Auer rods ± < 1 × 10 ⁹ /L monocytes	Unilineage or multilineage dysplasia 10% to 19% blasts Auer rods ±
Myelodysplastic syndrome, unclassified (MDS-U)	Cytopenias No or rare blasts No Auer rods	Unilineage dysplasia in granulocytes or megakaryocytes < 5% blasts No Auer rods
MDS associated with isolated del(5q)	Anemia < 5% blasts Platelets normal or increased	Normal to increased megakaryocytes with hypolobated nuclei < 5% blasts No Auer rods Isolated del(5q)

Appendix 4. Diagnostic Criteria for Chronic Myelomonocytic Leukemia (CMML)*

- Persistent peripheral blood monocytosis greater than $1 \times 10^9/L$;
- No Philadelphia chromosome or *BCR/ABL* fusion gene;
- Fewer than 20% blasts* in the blood or bone marrow;
- Dysplasia in one or more myeloid lineages. If myelodysplasia is absent or minimal, the diagnosis of CMML may still be made if the other requirements are present and: an acquired, clonal cytogenetic abnormality is present in the marrow cells, or the monocytosis has been persistent for at least 3 months and all other causes of monocytosis have been excluded;
- Diagnose CMML-1 when blasts fewer than 5% in blood and fewer than 10% in bone marrow;
- Diagnose CMML-2 when blasts are 5% to 19% in blood, or 10% to 19% in marrow, or if Auer rods are present and blasts are fewer than 20% in blood or marrow;
- Diagnose CMML-1 or CMML-2 with eosinophilia when the criteria above are present and when the eosinophil count in the peripheral blood is greater than $1.5 \times 10^9/L$.

*In this classification of CMML, blasts include myeloblasts, monoblasts, and promonocytes.

Appendix 5. Response Criteria and Progression Definitions for Myelodysplasia and CMML

Response Criteria	Peripheral Blood				Bone Marrow Blasts (BMB) (%)	Other
	Hgb (g/dL)	Neutrophils (L)	Platelets (L)	Blasts (%)		
Complete Remission	≥11	≥1 x 10 ⁹	≥100 x 10 ⁹	0	≤5	Normal maturation of all cell lines, note if has persistent dysplasia
Partial Remission					Decreased by ≥50% but still >5%	All CR criteria if abnormal before treatment except BMB
Marrow CR	If hematologic improvement (HI) response, note in addition to Marrow CR				≤5% & decreased by ≥50%	
Stable Disease						Failure to achieve PR & no evidence of progression*
Failure						Death, or disease progression: worsening cytopenia, increase in % BM blasts, progression to a more advanced MDS FAB subtype
Relapse after CR or PR						At least one of the following: Return to pre-treatment BMB % Decrement of ≥50% from maximum remission/response levels in granulocytes or platelets Reduction in Hb ≥1.5g/dL or transfusion dependence

*SD must last > 8 weeks but response is documented regardless of duration.

Additional Response Criteria for Myelodysplasia and CMML

Cytogenetic Response Complete	Disappearance of chromosomal abnormality with no appearance of new ones
Partial	≥50% reduction of chromosomal abnormality
Disease Progression For patients with % blasts at screening: <5% bone marrow blasts 5-10% bone marrow blasts 10-20% bone marrow blasts 20-30% bone marrow blasts For all categories, any of:	≥50% increase to >5% bone marrow blasts ≥50% increase to >10% bone marrow blasts ≥50% increase to >20% bone marrow blasts ≥50% increase to >30% bone marrow blasts At least 50% decrease from maximum remission/response in granulocytes or platelets Reduction in Hgb by ≥2 g/dL Transfusion dependence

Proposed modified IWG Myelodysplasia and CMML Response Criteria for Hematologic Improvement (HI)**

Erythroid response (pre-treatment <11g/dl)*	Hb increase by ≥1.5 g/dl Relevant reduction of units of RBC transfusions by an absolute number of at least 4 RBC transfusions/8 weeks as compared to the pretreatment transfusion number in the previous 8 weeks (only RBC transfusions given for Hb≤9/dL pretreatment will count in the RBC transfusion evaluation).
Platelet Response (pretreatment <100 x10 ⁹)*	Absolute increase of ≥30 x10 ⁹ /L if starting with >20 x 10 ⁹ /L platelets Increase from <20 x 10 ⁹ /L to >20 x10 ⁹ /L and by at least 100%
Neutrophil Response (pretreatment <1x10 ⁹ /L)*	At least a 100% increase and an absolute increase >0.5 x10 ⁹ /L
Progression or relapse after HI in the absence of another explanation	At least one of the following: At least 50% decrease from maximum response levels in granulocytes or platelets; Reduction in Hgb by ≥1.5g/dL; Transfusion dependence

*Pretreatment counts averages of at least 2 measurements (not influenced by transfusions) ≥1 week apart.

** Hematologic Improvement must last ≥ 8 weeks and is derived based on lab data entered in the database.

Appendix 6. 2008 WHO Diagnostic Criteria for Primary Myelofibrosis*

Major Criteria	
1. Megakaryocyte proliferation and atypia[†] accompanied by either reticulin and/or collagen fibrosis, or In the absence of reticulin fibrosis, the megakaryocyte changes must be accompanied by increased marrow cellularity, granulocytic proliferation and often decreased erythropoiesis (i.e., pre-fibrotic PMF).2. Not meeting WHO criteria for CML, PV, MDS, or other myeloid neoplasm.3. Demonstration of JAK2^{V617F} or other clonal marker, or no evidence of reactive marrow fibrosis.
Minor Criteria	
1. Leukoerythroblastosis2. Increased serum LDH3. Anemia4. Palpable splenomegaly

Abbreviations: CML, chronic myeloid leukemia; LDH, lactate dehydrogenase; MDS, myelodysplastic syndrome; PMF, primary myelofibrosis; PV, polycythemia vera; WHO, World Health Organization.

*Diagnosis requires meeting all three major criteria and two minor criteria.

†Small to large megakaryocytes with an aberrant nuclear/cytoplasmic ratio and hyperchromatic and irregularly folded nuclei and dense clustering.

Appendix 7. Response Criteria and Progression Definitions for Myelofibrosis

Response Criteria	Peripheral Blood				BM Blasts (%)	Other
	Hgb (g/L)	Neutrophils (L)	Platelets (L)	Other		
Complete Remission (CR)	≥110	≥1 x 10 ⁹	≥100 x 10 ⁹	All ≤ULN	≤5%	Complete resolution of disease-related symptoms & signs including hepatosplenomegaly. Normal leukocyte differential. Bone marrow histologic remission including osteomyelofibrosis Grade ≤1
Major Cytogenetic Response						This is a failure to detect a cytogenetic abnormality if pre-existing
Minor Cytogenetic Response						≥ 50% reduction in abnormal metaphases
Partial Remission (PR)	≥110	≥1 x 10 ⁹	≥100 x 10 ⁹	All ≤ULN		All CR criteria except for bone marrow histologic remission. A repeat bone marrow biopsy is required.
Clinical Improvement (CI)						In the absence of both PD & CR/PR requires one of the following for ≥8 weeks (over any 8-week period): - ≥20g/L increase in Hgb, or becoming transfusion independent (baseline <100 g/L). - either ≥50% reduction in splenomegaly of >10 cm or palpable at >5 cm at baseline and becomes not palpable. - Minimum 100% increase in ANC and ANC ≥ 0.5 x 10 ⁹ /L if baseline neutrophil <1x 10 ⁹ /L - Minimum 100% increase platelet count and absolute platelet count of 50,000x10 ⁹ /L if baseline <50x10 ⁹ /L
Progressive Disease (PD)						One of the following: - progressive splenomegaly* - leukemic transformation confirmed by bone marrow blasts >20% - >20% increase peripheral blood blast lasting >8 wks
Stable Disease (SD)						None of the above
Relapse						Loss of CR, PR or CI

* Progressive splenomegaly that is defined by the appearance of a previously absent splenomegaly that is palpable at greater than 5 cm below the left costal margin or a minimum 100% increase in palpable distance for baseline splenomegaly of 5-10 cm or a minimum 50% increase in palpable distance for baseline splenomegaly of greater than 10 cm.

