- Potential biomarkers of target modulation, response or resistance to PF-04449913 in combination with azacitidine in Japanese patients with previously untreated AML who are eligible for non-intensive chemotherapy;
- Objective disease response, as assessed using the appropriate response criteria for AML; duration of response; time to response

Continuation Cohort (Monotherapy Cohort):

- Type, severity (graded by NCI CTCAE, Version 4.0), timing, seriousness, and relatedness of adverse events; laboratory test abnormalities.

Efficacy-related data will not be collected in this cohort.

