4.1.1. Monotherapy Cohort

1. Patients with selected advanced hematologic malignancies who are refractory, resistant or intolerant to prior therapies. Eligible patients are limited to 1. Myelodysplastic Syndrome (any MDS International Prognostic Scoring System or IPSS score), 2. Myelofibrosis, 3. Chronic Myelomonocytic Leukemia (CMML), 4. CML T315I mutants, 5. CML in whom the T315I mutation is not present (any phase; must have received at least one prior treatment), 6. Acute Myeloid Leukemia (AML).
2. Patients with CML:
 - a. Must have a confirmed diagnosis as evidenced by the presence of the BCR-ABL translocation [t(9;22)] by fluorescence in situ hybridization (FISH), cytogenetics, or quantitative polymerase chain reaction (QPCR) for chronic myeloid leukemia in either chronic, accelerated or blast phase.
 - b. Non-T315I CML must have received at least one prior therapy.
 - c. May be resistant or intolerant as defined by:
 - In CML-CP, primary resistance is defined as failure to achieve a complete hematologic response (CHR) following 3 months on therapy; failure to achieve any cytogenetic response (CyR) following 6 months on therapy, failure to achieve a major cytogenetic response following 12 months on therapy, or failure to achieve a complete cytogenetic response following 18 months on therapy;
 - Secondary resistance is defined as a loss of CHR (defined by leukocytosis confirmed with at least one WBC>15K not felt to be due to a secondary cause); loss of a MCyR (defined by $\geq 30\%$ increase in the number of metaphases); or disease progression to AP or BP;
 - In CML-AP or CML-BP, resistance is defined as the failure to achieve a hematologic response, an increasing WBC, or an overt disease progression.

- Intolerance for all phases is defined as discontinuation of prior therapy due to adverse events at the lowest approved dose or if a patient can only tolerate prior therapy at less than the lowest approved dose.
 - In addition, for all phases (except patients with T315I mutations), patients are eligible in the case of unsatisfactory clinical response to the initial course of TKI, but who do not meet the definition for refractory, resistant or intolerant (eg, a CML CP patient who rapidly progresses on primary therapy, but does not meet the criteria for primary resistance because they have not been on TKI for 3 months; or patients with co-morbid diseases who cannot tolerate TKI therapy).

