Appendix 3. Response Criteria for Myelofibrosis

Objective response and Disease Progression

The objective status at each visit is determined per investigator evaluation (Protocol Appendix 7). However, the status will be verified per clinical judgment by the Sponsor. More specifically, the following categories on the CRF page will be considered objective response and disease progression for the purpose of this study.

Objective Response

Disease status assessments (if available)

- Complete remission (CR);
- Partial remission (PR);
- Clinical improvement (CI).

Cytogenetic response (if available)

- Major cytogenetic response;
- Minor cytogenetic response.

Objective Disease Progression

Disease status assessments (if available)

- Progressive disease (PD);
- Relapse.

Cytogenetic response (if available)

- Loss of cytogenetic response.

Relapse

Disease status assessments (if available)

- Relapse.

Cytogenetic response (if available)

- Loss of cytogenetic response.

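### The platelet route to Clinical Improvement in myelofibrosis is set 1,000 times above its own baseline cut-off, so this one of the four routes cannot be met as written

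*Protocol*

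**What the plan says.** The MF table in Protocol Appendix 7 defines CI by a list of alternatives: "In the absence of both PD & CR/PR requires one of the following for ≥8 weeks". The four alternatives are haemoglobin or transfusion independence, spleen size, neutrophils and platelets. The platelet alternative reads "Minimum 100% increase platelet count and absolute platelet count of 50,000x10" with exponent 9 per litre, that is 50,000 × 10⁹/L. It applies "if baseline <50x10" with the same exponent and unit, that is below 50 × 10⁹/L. The complete and partial remission rows of the same table ask for platelets of at least 100 × 10⁹/L.

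SAP Appendix 3 takes MF status from that table: "The objective status at each visit is determined per investigator evaluation (Protocol Appendix 7". It then has the sponsor verify the status on clinical grounds. Its list of objective responses includes "Clinical improvement (CI" and repeats no platelet figure.

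Patients with MF can enter the Monotherapy Cohort; Protocol section 4.1.1 lists "2. Myelofibrosis, 3. Chronic Myelomonocytic Leukemia (CMML" among the eligible diseases. Protocol section 2.2 makes objective disease response a secondary endpoint of that cohort. For the single MF patient in the Continuation Cohort, the same section states "Efficacy-related data will not be collected in this cohort".

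**The concern.** CI is a lesser response than complete or partial remission, yet its platelet bar stands far above theirs. The line also contradicts itself: it asks for a doubling and, in the same breath, for a count that no doubling from below 50 × 10⁹/L could approach.

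The SAP adopts the definition without correcting it, so this is live endpoint text. Read literally, a patient whose platelets meet the doubling and hold for eight weeks, with no other improvement, is not a responder. Read with a silent correction, the classification rests on a figure that stands nowhere in the plan, and the sponsor's verification has no usable written value to check against. There is a knock-on effect: Appendix 7 defines relapse as loss of complete remission, partial remission or CI, so a platelet improvement that was never recorded as CI cannot later be recorded as lost.

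**Working it through.** The plan derives no figure here. The threshold is a stated value, so the check is one of units and ratios within the documents.

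**Inputs**
- CI platelet threshold: 50,000 × 10⁹/L (Protocol Appendix 7)
- Baseline cut-off in the same line: below 50 × 10⁹/L (Protocol Appendix 7)
- Relative increase in the same line: at least 100%, that is 2-fold
- Complete and partial remission platelet level: at least 100 × 10⁹/L (Protocol Appendix 7)
- Neutrophil alternative: "Minimum 100% increase in ANC and ANC ≥ 0.5 x 10" (exponent 9 per litre), for a baseline below 1 × 10⁹/L (Protocol Appendix 7)
- Platelet ceiling for complete hematologic response in CML, unless related to therapy: 450 × 10⁹/L (Protocol Appendix 9)

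**Step 1: ratios**
- To the baseline cut-off: 50,000 / 50 = 1,000
- To the remission level: 50,000 / 100 = 500
- To the CML ceiling: 50,000 / 450 = 111
- In the neutrophil line, threshold to cut-off: 0.5 / 1 = 0.5. There the two figures are of the same order.

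**Step 2: rise required as written.** A patient with baseline b (in 10⁹/L) must reach the larger of 2b and 50,000. For every b below 50 the second term governs.

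| Baseline b | Count required | Fold rise = 50,000 / b |
|---|---|---|
| 10 | 50,000 | 5,000 |
| 20 | 50,000 | 2,500 |
| 40 | 50,000 | 1,250 |
| 49 | 50,000 | 1,020 |

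Every eligible patient needs more than a 1,000-fold rise, against the 2-fold rise in the same line.

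**Step 3: a possible source.** Appendix 7 gives platelets per litre, while Appendix 8 (AML) gives them per microlitre, for example 100,000/µL. Converting: 50,000/µL × 10⁶ µL/L = 50 × 10⁹/L, exactly the baseline cut-off. On that reading the patient must reach the larger of 2b and 50:

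| Baseline b | Count required |
|---|---|
| 10 | 50 |
| 20 | 50 |
| 25 | 50 |
| 30 | 60 |
| 40 | 80 |
| 49 | 98 |

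All of these lie below the remission level of 100 × 10⁹/L, as one would expect of a lesser response. The reading is coherent, but it remains an inference.

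**Step 4: one patient under both readings.** Platelets rise from 30 to 70 × 10⁹/L and stay there for eight weeks, with no progression, no remission and no other improvement. The relative rise is 70 / 30 = 2.3-fold, so the doubling is met. As written, 70 is below 50,000: no CI. On the step 3 reading, 70 exceeds 60: CI.

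**The case against.** The strongest reply is that this is an evident misprint with little consequence, and much of that stands.

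- **Other routes remain.** A reader might infer that CI, or objective response in MF, cannot be reached at all. The documents do not support that. Three CI alternatives are intact, and SAP Appendix 3 also counts complete remission, partial remission, and major or minor cytogenetic response. The patient in step 4 loses responder status only because platelets are the sole improvement.
- **Human judgment intervenes twice.** The investigator assigns status and the sponsor verifies it, so mechanical use of the printed figure is unlikely. This lowers the risk but does not supply a written threshold.
- **No estimate or test moves.** For this cohort, Protocol section 9.3 and SAP section 8.2.2 plan listings of disease status only. No MF response rate is planned that the error could push to zero.
- **It may come late.** Protocol section 1.2.8 reports 45 patients already treated out of at most 49, and the combination cohorts followed confirmation of monotherapy tolerability. A correction would probably not change any monotherapy assessment prospectively.

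A reader might also try to size the problem from B1371001, where 2 of 7 MF patients reached clinical improvement and MF made up 7 of 47 patients (15 × 7/47 = 2.2 for a cohort of 15). That does not work. The protocol does not say that either improvement was in platelets. The case mix of a Western study need not carry over, and the route also requires a baseline below 50 × 10⁹/L.

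What survives is the text itself: the printed figure is wrong on its face and the SAP adopts it.

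**Conclusion.** The point holds in a narrow form. One of the four routes to CI in MF cannot be met as written, because its threshold is 1,000 times the baseline cut-off beside it and 500 times the remission level in the same table. That no patient could reach such a count rests on general knowledge of platelet counts; the ratios in step 1 are the support within the documents.

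The effect is confined to Monotherapy Cohort patients with MF, a baseline below 50 × 10⁹/L and improvement in platelets only. The documents do not give their number, and it may be zero. The DMR test in the Expansion Cohort concerns AML and MDS and is unaffected, as is the Continuation Cohort.

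A reader might take 50 × 10⁹/L as the established intended value. It fits the line, but neither document states it, and the criteria cited under the table are not part of the plan. The sponsor has to confirm it. This is a minor, editorial correction to the definition of a secondary endpoint.

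**What to change.** 1. Reconcile the two platelet figures in Protocol Appendix 7 against the response criteria cited beneath the table, and restate the threshold in one unit. If the sponsor confirms 50,000/µL, that is 50 × 10⁹/L. Protocol section 6.4 lists relapse among the possible reasons for withdrawing study treatment, and loss of CI is relapse, so the value should come from that reconciliation and not from a guess in the analysis.
2. Record the result in a protocol amendment or, if none is planned, in a note to SAP Appendix 3.
3. Check whether the MF response page of the CRF, which is not among these documents, repeats the figure.
4. In the listings, confirm the classification of any MF patient in the Monotherapy Cohort with baseline platelets below 50 × 10⁹/L, and say in the study report which threshold was applied.

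The cost is one figure, one note and a look at a few listing rows. No sample size, test or table changes.

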Appendix 8. Response Criteria and Progression Definitions for Acute Myeloid Leukemia

Hematologic Responses to Treatment

Response Criteria	Neutrophils (µL)	Platelets (µL)	Bone Marrow Blasts (%)	Other
Morphologic Complete Response (CR) This is morphologic leukemia-free plus neutrophil & platelet response	≥1,000	≥100,000	<5 with spicules present, no Auer rods	Transfusion independent, no EMD
Morphologic CR with incomplete blood count recovery (CRi)	<1,000 -or-	<100,000	<5	Either neutrophils or platelets not recovered, no EMD. Elderly AML (>60 years) may be in a clinical CR with persistence of a cytopenia (usually neutropenia or thrombocytopenia)
Morphologic leukemia-free state	<1,000 -and-	<100,000	<5 blasts in BM with spicules and no blasts with Auer rods	Neutrophils and platelets not recovered, Flow cytometry negative, No EMD
Partial remission (PR)	≥1,000	≥100,000	decrease to 5-25 & ≥50% decrease from start	Blasts ≤5% if Auer rod positive
Partial remission with incomplete blood count recovery (PRi)	<1,000 -or-	<100,000	decrease to 5-25 & ≥50% decrease from start	
Minor Response	NA	NA	≥25% decrease from start	
Stable Disease	NA	NA	Blasts stable ±25%	

There is no minimum requirement for bone marrow cellularity or hemoglobin concentration for response criteria

Cytogenetic Responses to Treatment

Response Criteria	Neutrophils (µL)	Platelets (µL)	Bone Marrow Blasts (%)	Other
Cytogenetic CR (CRc)	>1,000	>100,000	<5	Cytogenetics - normal, no EMD
Molecular CR (CRm)	>1,000	>100,000	<5	Molecular-negative, no EMD

Criteria for Treatment Failure

Definition	Criteria
TF due to resistant disease	Pt survives ≥ 7 days post chemo; persistent AML $>25\%$ blasts in blood or BM
TF due to aplasia	Pt survives ≥ 7 days post chemo; death while cytopenic with aplastic bone marrow
TF indeterminate cause	Pt dies <7 days post therapy; Pt dies >7 days post therapy with no PB blasts, but no bone marrow exam; Pt does not complete 1st course of therapy
TF due to morphologic relapse	Reappearance of blasts post CR in PB or $\geq 5\%$ blasts in bone marrow not attributed to another cause
TF due to molecular or cytogenetic relapse	Reappearance of molecular or cytogenetic abnormality

Modified from Cheson BD, Bennett JM, Kopecky KJ et al. Revised recommendations of the International Working group for diagnosis, standardization of response criteria, treatment on outcomes and reporting standards for therapeutic trials in acute myeloid leukemia. J Clin Oncol 2003; 21(24) 4642-4649.⁶²

